1) Protocol Title

Addressing Tobacco Health Disparities via Group Intervention

2) Objectives*

Purposes and aims: (1) Examine the effects of CBT for smoking cessation on perceived stress and depressive symptoms in a racially/ethnically diverse sample; (2) test the efficacy of CBT for eliminating smoking cessation disparities; and (3) Examine physiological distress as an underlying mechanism for the effects of CBT on racial/ethnic minority smokers (exploratory).

3) Background*

Significance: Tobacco smoking is robustly associated with significant morbidity and mortality, from conditions such as cancer, diabetes, cardiovascular disease, and hypertension. Pervasive smoking-related health disparities exist across racial/ethnic and socioeconomic status (SES) groups. The most established disparities are observed in comparisons of African Americans and Whites, though evidence demonstrates disparities across populations of smokers.

The importance of reducing tobacco-associated health disparities between cannot be understated. Racial/ethnic minority smokers are less likely to quit successfully, even in the context of treatment. Perceived stress and depressive symptoms are known barriers to smoking cessation, yet have virtually been ignored in the disparities literature.

Racial/ethnic minority smokers tend to have elevated distress levels, which may contribute to disparities in cessation and health. Cognitive behavioral therapy (CBT) for cessation addresses these concerns and has the potential to reduce or eliminate disparities. Our preliminary studies, conducted in our established research clinic, found race/ethnic differences in baseline perceived stress and depressive symptoms. Following CBT, these differences were no longer present. Moreover, the lack of disparity in cessation appeared to be driven by the positive change in stress and depressive symptoms. This study will be the first RCT to test the impact of CBT on smoking cessation disparities.

4) Inclusion and Exclusion Criteria*

Inclusion criteria for this study include: (1) self-identify as African American/Black, Hispanic (any race), or White non-Hispanic; (2) smoke at least 5 cigarettes/day or CO reading of at least 8 ppm; (3) be over age 18; and (4) speak/read English and/or Spanish.

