Assessments. At the baseline visit, eligible participants will provide written informed consent, and complete some or all of the baseline measures (described below). They may also be asked to complete intra-treatment assessments during the 8 sessions. Follow-up assessments (called “reunions”) may occur at the end-of-therapy (EOT), and 3, 6, and 12-month follow-ups. The full assessment (at baseline) may require approximately 90 minutes to complete. Intra-treatment assessments may require 5 minutes, and follow-ups may require 60 minutes. The questionnaires may be completed (fully or in part) electronically using iPads/computers or on paper. Skip patterns may be built into the measures to decrease participant burden. All items are voluntary, thus participants may select an answer for each item before moving forward, and will have the option of selecting ‘I would rather not say’ on the electronic version or skipping items as desired. Surveys in either electronic or paper format will use identification numbers rather than identifying information.

Participants may complete some or all of the following measures:

Questionnaires: A standard demographic questionnaire assessing race, ethnicity, nativity, age, education, employment status, health insurance, marital status, and number of children. Measures may also include current medications, medical history (e.g., diabetes, hypertension, chronic back pain, arthritis, emphysema, and asthma), height, weight, smoking history, nicotine dependence, readiness to quit smoking, perceived stress, depressive symptoms, alcohol use, ethnic discrimination, nicotine withdrawal and urges to smoke, social support, daily hassles, e-cigarette use, sleep quality, intervention evaluations, group cohesion, smoking pattern, history of substance dependence and treatment, and use of other tobacco products and pharmacotherapies.

Bio-verification: Saliva cotinine levels may be assessed at baseline, and to confirm self-reported cessation at the 3, 6, and 12-month follow-ups. Research staff will be trained in the U.S. Centers for Disease Control (CDC) guidelines for transport of biological

specimens within the United States. The CBT intervention includes carbon monoxide (CO) testing at each treatment session to provide immediate feedback to participants regarding the benefits of cessation.

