Salivary cortisol: At each assessment point, we may collect saliva samples for cortisol analyses. Participants who agree will be provided with the needed materials and trained in saliva collection procedures at orientation and prior to assessments. They may be asked to collect saliva up to 4 times throughout the day. Saliva samples will be stored in the lab freezers. At the time of collection, we will ask participants to record hours of sleep, food consumption, and exercise within the past hour.

Randomization. Participants may be randomly assigned to one of 2 conditions. In the first condition, *Group Cognitive Behavioral Therapy for Smoking Cessation (CBT)*, participants may receive 8 group sessions and eight weeks of TNP [21mg (4 weeks), 14mg (2 weeks), and 7mg (2 weeks)]. The four-week CBT protocol includes 4 sessions during week 1, 2 sessions during week 2, 1 session during week 3, and 1 session during week 4. We will request that participants attend every session; however, we recognize that this will not always be feasible. CBT is intended to guide participants through the cessation process and teach relapse prevention skills. Sessions may include a functional analysis of smoking patterns, environmental cues, and motivation for change, and cover nicotine addiction and withdrawal, health consequences, benefits of cessation, stress management, negative affect, alcohol use, triggers, coping responses, cognitive restructuring, social support, decision making, weight control, and physical activity. In the second condition, *General Health Education*, participants may receive sessions including didactic information on tobacco-associated morbidities, such as heart disease, diabetes, and hypertension. Content may include PowerPoint-delivered lectures on the prevalence, etiology, basic pathology, symptom patterns, and treatment of the conditions, and discussion questions designed to facilitate learning and interest. Smoking cessation specific topics will not be addressed, and coping skills will not be provided. Participants will be allowed to share feelings regarding smoking (if they mention them) and general questions will be answered, although no specific behavioral quitting advice will be provided (i.e., they will be encouraged to adhere to the TNP protocol). The groups in both conditions are expected to require 90-120 minutes, depending on group size. Sessions may be audio or video taped.

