Participants will be paid for completing assessments, baseline (\$20), EOT (\$30), 3-month (\$40.00), 6-month (\$50.00), and 12-month (\$50.00), prorated by half for incomplete assessments. Funds permitting, participants may also receive reimbursement for transportation and light refreshments during visits. We anticipate that data collection may occur within a 4-year period, although this may vary depending on recruitment progress.

5) Data and Specimen Banking*

N/A

6) Data Management*
Statistical Analysis

Descriptive statistics such as frequencies, percentages, means, medians, standard deviations, and interquartile ranges may be tabulated to describe the study sample.

Associations between variables and intervention effects may be assessed with Wilcoxon/Kruskal-Wallis tests, Chi-squared/Fisher exact tests, analyses of variance, multiple regression, generalized linear mixed models, and logistic regression.

Data may be collected using the University of Miami Qualtrics survey program and stored on password-protected university servers. Surveys collected on paper will be entered by members of the research team into password protected data files. Access to the files containing the survey and survey responses is restricted and only study personnel will be given access to these files. Identifying information will not be collected with electronic or paper questionnaires. Data published from this survey will be presented in group form, so that individual participant data is not identifiable. Data may be stored for up to five years following publication of findings.

Guidelines for Adverse Events (AEs) and Smoking Cessation Rates

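### Aim 1 has no named analysis and no therapy-group effect, so several listed tests, run in their standard form, would overstate precision for scores from participants treated in groups

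*Combined protocol and SAP*

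**What the plan says.** Aim 1 in section 2 (Objectives) is to "Examine the effects of CBT for smoking cessation on perceived stress and depressive symptoms in a racially/ethnically diverse sample".

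Under Procedures Involved, Randomization, participants are assigned to one of two conditions. In the CBT condition "participants may receive 8 group sessions". The same paragraph gives an expected session length for the groups in both conditions and says it depends on group size, so General Health Education is also delivered in groups. Group size is not given. Under Assessments, the list of possible questionnaires includes "intervention evaluations, group cohesion, smoking pattern", so the study may itself measure how the groups function.

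The inferential plan is one sentence in section 6 (Data Management, Statistical Analysis): associations and "intervention effects may be assessed with Wilcoxon/Kruskal-Wallis tests, Chi-squared/Fisher exact tests, analyses of variance, multiple regression, generalized linear mixed models", with logistic regression closing the list. No method is assigned to Aim 1. Therapy group is not mentioned as a factor, random effect or cluster in any analysis. Adjustment for the baseline score is neither specified nor excluded.

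**The concern.** Participants who attend the same sessions share a leader, a peer group and a schedule, so their later stress and depression scores may be correlated. Both arms consist of such groups. The variance of the arm difference then includes a between-group part that a single-level test does not estimate correctly.

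An analyst could follow section 6 to the letter, choose a Wilcoxon test, a one-way ANOVA or an ordinary regression for Aim 1, and report an interval that is too narrow. An effect of CBT on stress or depressive symptoms would then be declared more often than 5% of the time when there is none. For a given group size and ICC, enrolling more participants does not reduce the excess, because it depends on group size and not on total sample size.

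**Working it through.** **Plan's own figure.** There is none to reproduce. The documents give no alpha, power, ICC or sample-size derivation.

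**Inputs.**
- From the documents: random assignment of participants to two conditions; group delivery in both arms; the list of methods.
- Assumed: 1:1 allocation; two-sided 5% level; m = 6 to 10 analysed per group; ICC = 0 to 0.05; correlation between baseline and follow-up score r = 0.3 to 0.7.

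**Step 1: no baseline adjustment.** Set the total variance to 1 and the between-group variance to ICC. The true variance of the arm difference, divided by the variance that a single-level test assumes, is

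DE = 1 + (m − 1) × ICC,

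and the actual false-positive rate is 2 × Φ(−1.960 / √DE).

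| ICC | m = 6: DE, rate | m = 8: DE, rate | m = 10: DE, rate |
|---|---|---|---|
| 0 | 1.00, 5.0% | 1.00, 5.0% | 1.00, 5.0% |
| 0.01 | 1.05, 5.6% | 1.07, 5.8% | 1.09, 6.0% |
| 0.02 | 1.10, 6.2% | 1.14, 6.6% | 1.18, 7.1% |
| 0.05 | 1.25, 8.0% | 1.35, 9.2% | 1.45, 10.4% |

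For example, with m = 10 and ICC 0.05, √1.45 = 1.204 and 1.960 / 1.204 = 1.628, which gives 10.4%. The correct interval is wider by the factor √DE: from 1.025 (m = 6, ICC 0.01) to 1.204 (m = 10, ICC 0.05).

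**Step 2: baseline added by ordinary regression, no group effect (conditional).** If participants are individually randomized and the groups form afterwards, the baseline score reduces the residual variance to 1 − r² but leaves the group variance in place:

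DE = 1 + (m − 1) × ICC / (1 − r²).

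With m = 8:

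| ICC | no baseline | r = 0.3 | r = 0.5 | r = 0.7 |
|---|---|---|---|---|
| 0.02 | 6.6% | 6.8% | 7.2% | 8.3% |
| 0.05 | 9.2% | 9.6% | 10.6% | 13.1% |

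Defining r within groups, and not on the total variance, changes these figures slightly (12.8% in place of 13.1% in the last cell).

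**Step 3: simulation of the listed tests.** In 6,000 null trials per setting (N = 480, m = 8, ICC 0.05, correlation 0.6 within groups), ANOVA rejected in 9.8%, the Wilcoxon test in 9.0% and regression with baseline in 11.1%. The closed form for these settings gives 9.2% without baseline and 11.3% with it. At ICC 0 the three tests rejected in 5.1–5.6%.

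**Step 4: methods that account for group.** A group-level analysis adjusted for baseline, which stands in for a random group effect when groups are of equal size, rejected in 4.8%, 5.0% and 5.5% at ICC 0.02, 0.05 and 0.10 (m = 8, correlation 0.6). Regression with baseline and group-robust standard errors, with 25 groups of 10 per arm, rejected in 5.2–5.8%. A full longitudinal mixed model was not simulated.

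**Step 5: when Step 2 reverses.** If whole cohorts were randomized and baseline scores clustered by group, baseline adjustment would lower the error. In simulation (m = 8, baseline ICC 0.10) the rate fell from 12.9% to 11.3% at ICC 0.05, and from 8.4% to 5.9% at ICC 0.01.

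**The case against.** The strongest reply is that the plan commits to nothing invalid. Its list is permissive and includes generalized linear mixed models, which can carry a therapy-group random effect. That is true, and it limits the point: the gap is that the group effect is neither named nor required. It does not remove the point, because the list equally permits tests that ignore group.

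A second reply is that the size rests on assumptions. This also stands. At ICC 0.01 the excess is at most about one percentage point without baseline adjustment, and at ICC 0 there is none. The further rise with baseline depends on a choice the plan has not made, and it is only 0.2 to 0.6 points at ICC 0.02, m = 8 and r of 0.3 to 0.5.

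Three stronger readings are tempting and are not supported:
- A reader might infer that only the mixed model can use the baseline score and hold the error rate. ANOVA can use baseline too, through change scores or repeated measures, and regression with group-robust errors stays near 5%.
- A reader might infer that only precision is affected and the CBT estimate is unbiased in any case. The Assessments section makes all items voluntary, so scores may be missing, and unbiasedness would need an assumption that the plan does not state.
- A reader might take "Following CBT, these differences were no longer present" in section 3 as making end of therapy the deciding visit. That sentence reports race/ethnic differences in preliminary studies. It is not the Aim 1 contrast between arms and names no visit.

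**Conclusion.** The point holds as a specification gap with a real consequence: tests that the plan allows for Aim 1 would be anti-conservative if scores correlate within therapy groups. With 6 to 10 analysed per group, a nominal 5% test without baseline adjustment would reject in about 5.6–6.0%, 6.2–7.1% and 8.0–10.4% of null trials at ICC 0.01, 0.02 and 0.05. Adding baseline by ordinary regression under individual randomization raises this further: with groups of 8, to 6.8–8.3% at ICC 0.02 and 9.6–13.1% at ICC 0.05 for r of 0.3 to 0.7.

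The mechanism is certain once the ICC is above zero. The size is not, because group size, ICC, r, allocation and test level are all assumed. The rise with baseline is not an argument against baseline adjustment; it is a reason to put baseline and therapy group into the analysis together. The calculation covers the contrast between arms, not comparisons of race/ethnic groups within therapy groups. The change should be made, because it is cheap and the choice of method is better fixed before results are seen.

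**What to change.** For each of the two Aim 1 scales, specify one analysis that adjusts for the baseline score and accounts for therapy group. The preferred choice is the mixed model already on the list, with a therapy-group random effect and small-sample degrees of freedom based on the number of groups. Regression with baseline and group-robust standard errors is an acceptable alternative. State that tests ignoring therapy group do not carry the Aim 1 conclusion. Record a therapy-group identifier for every participant, since it may be hard to recover later.

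The cost is one paragraph in section 6, one recorded field and somewhat wider, correct intervals. No extra participants are needed to make the analysis valid. The deciding visit, the covariance structure over visits, any constraint on baseline means, and a firm commitment to collect both scales at every assessment are separate choices that do not follow from this point.

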Participant recruitment may occur using several methods, including radio and newspaper stories and advertisements, community events (e.g., health fairs), neighborhood canvassing, email, online social-media and advertising sites, and flyers and post-cards distributed throughout the community (e.g., churches, Laundromats, businesses, physicians’ offices, health centers/clinics). Recruitment may also take place at other medical sites (e.g., Broward Health organization, and UHealth regional sites) through patient referrals, community outreach, or direct referrals to the Research staff. After calling the telephone

number provided in the advertisements or being identified in person, RAs may explain the study to participants (paraphrasing from a script) and conduct screening for eligibility.

Participants may be given small tokens of appreciation, such as water bottles, wallets, or bags.

15) Local Number of Subjects

We anticipate screening up to 1000 subjects and enrolling up to 500 to complete the study. Moffitt Cancer Center will enroll 150 subjects. Moffitt's enrollment numbers are not included in this protocol, being as it is stated in their own IRB protocol.

16) Confidentiality

Contact information for participants scheduling appointments to participate on site may be recorded over the telephone and stored in a password encrypted database. Following study completion, contact information may be deleted from the database. Only the PI and study personnel may have access to the database. Survey data may be collected and stored on University of Miami and H. Lee Moffitt Cancer Center password protected servers using electronic survey software. Assessment responses will not include identifying information. Only select study personnel may have administrative access to the survey data. Personnel with access must log onto the system with a username and password. Data may be maintained for five years post study publication.

17) Provisions to Protect the Privacy Interests of Subjects

Study participation is completely voluntary and confidential, which is explained during the informed consent process. Several RAs will recruit, schedule, and collect information from participants. They may elect to interact with (or not) any of the study staff. The questionnaires may be self-administered; however staff will be available to assist participants as needed. If desired and space-permitting, participants may be allowed to complete the assessment in private.

18) Consent Process

Participants will undergo screening for enrollment into the study. We are requesting a waiver of documentation of consent for this portion only as it is done via phone or in person; however, this is minimal risk and consent is not required outside of the research setting to ask the screening questions.

Informed consent may be obtained prior to confirming eligibility to participate in the study during the baseline visit. Consent will be obtained by the PI or key personnel (trained Research Associates and clinical psychology graduate students).

19) Process to Document Consent in Writing

Participants will be given an informed consent form. Study staff will be available to explain the assessments to participants and answer any questions they have about participation. Participants will be provided with copies of the consent document.

20) Data & Safety Monitoring Committee Oversight

The Sylvester Comprehensive Cancer Center (SCCC) Data and Safety Monitoring Committee (DSMC) will monitor this clinical trial according to the Cancer Center's Data and Safety Monitoring Plan (DSMP). In its oversight capacity, the DSMC bears responsibility for suspending or terminating this study.

DSMC oversight of the conduct of this trial includes ongoing review of adverse event data, and periodic review of self-reported smoking cessation rates. The guidelines appearing in Section #6 are offered for DSMC consideration in assessing adverse events and self-reported smoking cessation rates. In addition, the DSMC will review reports from all audits, site visits, or study reviews pertaining to this clinical trial and take appropriate action.

21) Monitoring, Auditing, and Inspecting

The investigator will permit trial-related monitoring, quality audits, and inspections by, government regulatory authorities, of all trial-related documents (e.g., source documents, regulatory documents, data collection instruments, case report forms). The investigator will ensure the capability for inspections of applicable trial-related facilities. The investigator will ensure that the trial monitor or any other compliance or QA reviewer is given access to all trial-related documents and trial-related facilities. Participation as an investigator in this trial implies the acceptance of potential inspection by government regulatory authorities.

22) Quality Assurance and Quality Control

In addition to the Clinical Monitoring component of this protocol, Quality Assurance (QA) will be implemented to assess compliance with GCP and applicable regulatory requirements. Data or documentation audited shall be assessed for compliance to the protocol, accuracy in relation to source documents and compliance to applicable regulations.

23) Financing and Insurance

Not applicable.

24) Publications and Data Sharing

This study will comply with the NIH Data Sharing Policy and Policy on the Dissemination of NIH-Funded Clinical Trial Information and the Clinical Trials Registration and Results Information Submission rule. As such, this trial will be registered at ClinicalTrials.gov, and results information from this trial will be submitted to ClinicalTrials.gov. In addition, every attempt will be made to publish results in peer-reviewed journals. Data from this study will be made available upon written request 30 days after the publication acceptance of primary study findings. De-identified requests will be honored for a period of 3 years of anniversary date by contacting principal investigator, [name].
